6.3.10 Pharmacokinetics of Nasopharyngeal Samples

A nasopharyngeal swab will be collected from each nostril as described in Table 1 and Laboratory Manual. These swabs will be sent to a central virology laboratory for processing into appropriate aliquots for virology and PK analysis. Further details on sample collection, processing, shipment, and storage will be described in the Laboratory Manual.

Note: Nasopharyngeal samples taken from all subjects may be infectious and will be classified as “diagnostic specimens” for dispatch purposes.

6.3.11 Pharmacokinetics and Viral Load in Tracheal Aspirate

Tracheal aspirate will be obtained in subjects on mechanical ventilation, at the time points listed in Table 1. The samples will be sent to a central virology laboratory for processing into appropriate aliquots for virology and PK analysis. Samples for determination of the concentration of VIS410 will be analyzed under the responsibility of the Sponsor. Further details on sample collection, processing, shipment, and storage will be described in the Laboratory Manual.

Note: Tracheal samples taken from all subjects may be infectious and will be classified as “diagnostic specimens” for dispatch purposes.

6.3.12 Immunology

The immunology parameters under evaluation are the detection of ADA titers and anti-influenza A antibody titers by HAI.

Blood samples for immunology assessments will be collected according to the time points defined in Table 1. Blood samples will be collected by venipuncture or via indwelling cannula in the forearm into standard serum separator tubes. The exact date and time of blood sampling must be recorded in the EDC system. Further procedures for sample collection, shipment, processing, and storage will be described in the Laboratory Manual.

6.3.12.1 **Antidrug Antibody Response**

Anti-VIS410 antibody titers will be determined by Visterra or designee. These samples may be stored to assess anti-VIS410 antibodies with neutralizing capabilities in accordance with local regulations.

6.3.12.2 **Anti-Influenza Antibody Response**

Anti-influenza A antibody titers will be determined by Visterra or designee.

6.4 **Safety of Total Blood Sampling Volume**

The total volume of blood that will be drawn from each subject will be approximately 178 mL over the course of the study. In order to obtain additional information to ensure a subject's safety, additional blood samples (up to 50 mL) may be taken at the discretion of the Investigator.

6.5 **Safety Evaluations**

The safety assessment in this study will be based on AEs, clinical laboratory tests, vital signs, electrocardiography, and physical examination, as described in the following sections.

6.5.1 **Adverse Events**

Adverse events (AEs) will be monitored continuously from dosing until the last study-related activity. At regular intervals during the study, subjects will be asked non-leading questions to determine the occurrence of any AEs. All AEs reported spontaneously during the course of the study will be recorded as well.

Subjects will be observed during infusion and for at least 2 hours after the completion of administration of VIS410/placebo to allow monitoring for possible hypersensitivity reactions, anaphylactic reactions, or other AEs that occur during this time period.

All AEs will be recorded in the EDC system. For detailed definitions and reporting procedures of AEs (see Section 9.7).

6.5.2 **Injection Site Tolerability**

Injection site tolerability is defined as AEs demonstrating significant local injection site irritation or tissue damage.

6.5.3 **Complications of Influenza**

Complications of influenza are defined as pneumonia, myocarditis, worsening of chronic bronchitis, sinusitis, otitis or other chronic pulmonary diseases, encephalopathy, and death. Complications of influenza and use of antibiotic therapy for bacterial pneumonia will be reported by variable, treatment group, and time point. Diagnosis of bacterial pneumonia will be based on

local clinical practice, usually an assessment of clinical features and any radiographic evidence of bacterial pneumonia (eg, infiltrate) and/or microbiologic evidence of bacterial pneumonia. All-cause and attributable mortality will be evaluated on Day 14 and Day 28.

6.5.4 Clinical Laboratory Tests

Blood samples will be collected by venipuncture or via indwelling cannula at the time points indicated in Table 1.

Appendix 14.2 lists the biochemistry, hematology, and coagulation tests that will be performed by the central laboratory on the safety blood samples. Note: subjects to be enrolled based on the Investigator's discretion including any local laboratory results per SOC at institution.

Creatine kinase-MB, creatinine kinase, and troponin are to be measured by the central laboratory in the event of a subject having chest pain. Subjects with chest pain should be managed per SOC.

In the event of a subject exhibiting the signs and symptoms of an anaphylactic reaction, when possible at the time of the event, a 5-ml serum sample should be collected for further assessment (ie, tryptase, chymase) to be measured by the central laboratory.

A midstream urine sample will be collected for the central laboratory for urinalysis by dipstick, flow cytometry, and microscopic examination. Appendix 14.2 lists the urinalysis parameters that will be assessed.

A serum pregnancy test will be performed by the central laboratory for all time points indicated in Table 1. In addition, a negative pregnancy test (serum or urine) result within 2 days prior to dosing must be available from the local laboratory prior to randomization.

For oseltamivir dosing, creatinine clearance (Cockcroft-Gault Equation) must be calculated using the serum creatinine value from the local laboratory prior to randomization.

The Investigator must review the laboratory report, document this review, and record any change occurring during the study he/she considers to be clinically relevant in the EDC system. Laboratory values outside the normal range will be flagged, and their clinical relevance will be assessed by the Investigator.

6.5.5 Vital Signs and Body Temperature

Vital sign parameters will be assessed after 5 minutes in supine position at the time points indicated in Table 1. The vital sign parameters that will be assessed are supine SBP, DBP, heart rate, and respiratory rate.

Any change from baseline in vital sign values occurring during the study that is considered to be clinically relevant by the Investigator should be recorded as an AE.

Oral body temperature will be recorded at the end of infusion then BID while in the hospital and then throughout the study according to the study procedures outlined in Table 1. In cases where obtaining oral temperature is not possible, core temperature (eg, tympanic, axillary) will be obtained.

While the patient is hospitalized, the maximum temperature should be recorded for each 12-hour interval (from 12 AM to 12 PM and from 12 PM to 12 AM). Fever is defined as a core body temperature $\geq 38^{\circ}\text{C}$.

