10.6.3 Time to Clinical Response

Time to clinical response is defined as resolution of 4 of 5 vital signs that will be determined upon physical examination. Clinical response is defined as:

- Afebrile with core temperature $\leq 37.8^{\circ}\text{C}$, without use of antipyretics (oral $\leq 37.2^{\circ}\text{C}$)
- Respiratory rate ≤ 24 beats per minute
- Oxygen saturation $\geq 95\%$ on room air without support or a return to pre-infection status, if pre-infection status was $< 95\%$
- Pulse rate $\leq 100/\text{min}$
- SBP ≥ 90 mm/Hg, without vasopressor use

The probability of time to clinical response (defined as resolution of vital signs) will be calculated via Kaplan-Meier. A significance test (using the log-rank test) for each VIS410 dose vs placebo will be presented. The number and percentage of subjects in each treatment group with clinical response will be summarized. Results will be tabulated and presented graphically as well.

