### 9.2.3 Time to Clinical Response

Time to clinical response (days) is defined as time to the finding of normality (as defined below) for 4 out of 5 vital signs that will be determined upon physical examination. Clinical response is defined as:

- Afebrile with core temperature  $\leq 37.8^{\circ}\text{C}$ , without use of antipyretics (oral  $\leq 37.2^{\circ}\text{C}$ )
- Respiratory rate  $\leq 24$  beats per minute
- Oxygen saturation  $\geq 95\%$  on room air without support or a return to pre-infection status, if pre-infection status was  $< 95\%$
- Pulse rate  $\leq 100/\text{min}$
- SBP  $\geq 90$  mm/Hg, without vasopressor use

For determination of time to clinical response, achievement of any of the criteria above will carry forward to missing data at subsequent visits. Subjects who do not experience clinical response will be censored at the last available vital sign visit date. Time to Clinical response will be analyzed using Kaplan-Meier techniques.

Pre-infection oxygen saturation data on room air status was not collected on the CRF. Therefore, prior to database lock, for any subject with persistent oxygen saturation on room air  $< 95\%$ , a query to the investigator will be sent to request historic oxygen saturation on room air data. If a baseline oxygen saturation on room air value collected during 6 months prior to enrollment is available, the information will be captured and recorded in a spreadsheet maintained by data management at POI. This spreadsheet will be reviewed, signed and locked prior to database lock. This information will be used to define pre-infection oxygen saturation on room air for the purposes of calculating time to clinical response. If there are no available medical record data and oxygen saturation remains below 95% on room air, the subject will be analyzed as not experiencing clinical response.

Note, the number of vital signs abnormalities (utilizing the above criteria) may range from 0 to 5 for subjects enrolled in the trial, although the expectation is that all subjects will have at least one abnormality. Therefore, this analysis will be conducted in two ways. First, the probability of time to clinical response (defined as the finding of at least 4 of 5 normal vital signs using the criteria above) will be calculated via Kaplan-Meier; under this analysis, some subjects will have met criteria for a clinical response at baseline. Time to clinical response will be calculated as Date of

January 17, 2019

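### Axillary temperature is classed as core, so it is judged against a limit 0.6 °C more lenient than oral and may score a febrile subject as afebrile for clinical response

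*Protocol*

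**What the plan says.** Protocol 6.5.5 makes oral the default route: "Oral body temperature will be recorded at the end of infusion then BID while in the hospital". Where that is not possible, "core temperature (eg, tympanic, axillary) will be obtained". The same section asks for the maximum temperature in each 12-hour interval in hospital and sets the only fever definition: "Fever is defined as a core body temperature" of 38 °C or more. Footnote 12 of the Schedule of Assessments repeats the switch from oral to core without naming sites.

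Protocol 10.6.3 states: "Time to clinical response is defined as resolution of 4 of 5 vital signs". The temperature sign is met at core ≤37.8 °C or oral ≤37.2 °C, without antipyretics. SAP 9.2.3 repeats the same pair of limits, with the oral figure in brackets after the antipyretic condition ("without use of antipyretics (oral"). SAP 9.2.3 also does two further things that matter here:

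- A criterion once met is carried into missing data at later visits.
- The analysis is repeated in subjects with more than two abnormal signs at baseline, counted by the same criteria.

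Neither document gives an axillary limit, an offset between routes, or a rule for analysing temperature by route. SAP 4.1 only converts Fahrenheit to Celsius, and the list of changed analyses in SAP 16.1 does not mention temperature.

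**The concern.** The two limits show that the plan expects core to read above oral. Placing axillary under core gives the higher limit to a site that the documents do not show to read that high. If axillary in fact reads below core, the temperature sign is met too easily for those readings.

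Three results are at stake. First, response may be dated too early when temperature is the sign that decides it. Second, a false afebrile call can persist through the carry-forward rule. Third, a falsely normal baseline temperature can remove a subject from the subset with more than two abnormalities. If the route changes during follow-up, for example from axillary to oral, the effective threshold changes within the subject. The study is meant to identify sensitive endpoints for Phase 3, so noise in the scoring of a candidate endpoint counts against that purpose.

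**Working it through.** The plan states no figure to reproduce. The check traces each route to its limit and then does arithmetic on the documents' own limits.

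**Inputs.** Core limit 37.8 °C and oral limit 37.2 °C (Protocol 10.6.3, SAP 9.2.3). Fever definition, core ≥38.0 °C (Protocol 6.5.5). Axillary shortfall below core, *d*: not in the documents, assumed to lie between 0 and 1.0 °C.

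**Step 1, route to limit.** Axillary is an example of core, and there are only two limits, so axillary is judged at 37.8 °C.

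**Step 2, gap between limits.** 37.8 − 37.2 = 0.6 °C. A reading above 37.2 and up to 37.8 °C meets the criterion by axilla and fails it by mouth.

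**Step 3, core temperature when the axillary reading is exactly at the limit.** Core = 37.8 + *d*.

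| Assumed *d* (°C) | Core at axillary 37.8 °C | Meets the fever definition? |
|---|---|---|
| 0 | 37.8 | No |
| 0.2 | 38.0 | Yes |
| 0.3 | 38.1 | Yes |
| 0.5 | 38.3 | Yes |
| 0.6 (the plan's own core–oral gap) | 38.4 | Yes |
| 1.0 | 38.8 | Yes |

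The break-even shortfall is 38.0 − 37.8 = 0.2 °C.

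**Step 4, readings affected.** A subject is febrile by definition but scored afebrile when the axillary reading lies between 38.0 − *d* and 37.8 °C. For *d* = 0.5 that is 37.5 to 37.8 °C; for *d* = 1.0 it is 37.0 to 37.8 °C.

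**Step 5, when temperature decides.** Response needs four of five signs. Inclusion criterion 4 requires oxygen support at entry, and the saturation sign requires room air without support (or return to a pre-infection level). While support continues, that sign generally cannot be met, so the other four, temperature included, must all be normal. In such a subject a false afebrile call can complete the response.

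**Step 6, baseline subset.** Entry needs at least three abnormal signs. A subject with exactly three, one of them temperature, falls to 3 − 1 = 2 if the axillary reading is scored normal, and leaves the subset.

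**The case against.** The strongest reply is that the decisive premise lies outside the documents: nothing in them says how axillary compares with core or oral. That stands. The label and the limit are read from the text, but the step from there to a febrile subject scored afebrile needs an assumed shortfall of at least 0.2 °C.

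A reader might infer that every axillary reading from 37.3 to 37.8 °C is misclassified. The documents do not support that. It would make the oral limit the correct axillary standard, which no section says. An oral 37.7 °C fails the afebrile criterion but is not fever by the protocol's definition either.

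A reader might also infer that the error concentrates in ventilated or the sickest subjects. That is plausible, but Protocol 6.5.5 says only that oral was not possible. It does not say who those subjects are, how many there are, or how often axilla is used rather than tympanic.

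Several limits on reach also stand. The sign fails under antipyretics whatever the route. Time is counted in dates, so within-day shifts disappear. Temperature matters only when it is the deciding or marginal sign. The 12-hour maximum protects against an isolated low reading, but it does not correct a systematic difference between sites.

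Finally, this is one component of one secondary endpoint in an unpowered, exploratory study whose p-values are informational. That lowers the stakes without making the rule sound.

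**Conclusion.** The point holds in a limited form. As written, the plan scores axillary readings at 37.8 °C, which is 0.6 °C more lenient than oral, and no rule elsewhere corrects this. It is a stated scoring rule that can give a wrong answer, and the Protocol's summary of changes for Amendment 1 shows that the site examples were added deliberately and match the current text. Under an assumed shortfall of 0 to 1.0 °C, the limit corresponds to a core temperature of 37.8 to 38.8 °C. The conflict with the protocol's own fever definition begins at 0.2 °C.

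The effect on results cannot be sized, because the number of axillary readings is unknown. It would be tempting to infer a bias in favour of one arm. The documents do not support that: with randomisation and blinded assessors, the error is probably similar across arms. The expected harm is some responses dated too early and a blurred treatment contrast in time to clinical response. The Day 7 ordinal primary endpoint does not use temperature and is untouched. The change should be made, but it does not threaten the main conclusions.

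**What to change.** - **Protocol 6.5.5:** remove axillary from the examples of core temperature.
- **SAP 9.2.3:** state that the core limit does not apply to axillary readings. For endpoint scoring only, either hold them to a limit no more lenient than the existing oral one, or treat them as not establishing the afebrile criterion. Prespecify one and run the other as a sensitivity analysis. The second is the safer check, since even at 37.2 °C an assumed shortfall of 38.0 − 37.2 = 0.8 °C or more would reach the fever definition.
- **Data:** confirm that the eCRF captures the site of each reading. The documents do not show this. If it does not, add the field or query sites before database lock. Without the site, the rule cannot be applied to readings already taken.

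The cost is a wording change, a few lines of programming and a small data-query effort. The downside is slightly later response times for subjects measured by axilla.

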6.5.6 Electrocardiography

Single, 12-lead ECGs will be performed after a 5-minute rest at the time points indicated in Table 1. The ECG parameters assessed are heart rate, PR interval, QRS interval, and QT interval. Values for QT corrected for heart rate (QTc) will be derived. QTc corrected according to Fridericia (QTcF) will be the primary correction parameter.¹³ QTc parameters can be calculated subsequently if not immediately available at the site.

Any change from baseline in ECG values occurring during the study that is considered to be clinically relevant by the Investigator should be recorded in the EDC system.

6.5.7 Physical Examination

A complete physical examination will be performed at the time points indicated in Table 1. Physical examination at screening will include height and weight. To obtain the actual body weight, subjects must be weighed at screening. The height should be measured barefoot, if possible. The screening physical examination will be complete; thereafter, targeted physical examinations may be performed at the discretion of the Investigator.

A complete physical examination includes examination of body systems (including, but not limited to, general appearance, skin, neck, eyes, ears, nose, throat, breast, lungs, heart, abdomen, back, lymph nodes, extremities, and nervous system).

The targeted physical examination should be focused, at the Investigator's discretion, based on the subject's condition and circumstances. The targeted physical examination should note any changes in the subject's condition (body systems) since the last assessment and does not preclude examination of any of the body systems as clinically indicated.

Any change in physical examination occurring during the study that is considered to be clinically relevant by the Investigator should be recorded as an AE.

6.5.8 Radiological Assessment

A baseline chest x-ray or CT scan will be performed for the assessment of pneumonia. However, a chest x-ray or CT scan performed as part of routine SOC within 72 hours before randomization will be acceptable. The results of any such studies will be recorded in the EDC.

6.6 Appropriateness of Measurements

The assessments that will be made in this study are standard, and are generally recognized as reliable, accurate, and relevant.

7.0 STUDY TREATMENTS

7.1 Test Product, Dose, Mode of Administration

The Investigator must ensure that the investigational product will be used only in accordance with the protocol. It is forbidden to use investigational drug material for purposes other than as defined in this protocol.

VIS410 (2000 mg or 4000 mg) will be administered IV over 2 hours as a single, 200-mL infusion, followed by a 25-mL (or volume equivalent to length of IV line) saline flush to ensure all product is administered, in addition to oseltamivir (Tamiflu) 75 mg BID for total of 5 days (10 doses). Treatment with oseltamivir may be extended for up to 5 additional days (up to 20 doses of total therapy) if clinical symptoms warrant further treatment as assessed by the Investigator. Note: based on SOC, subjects may have started oseltamivir therapy prior to randomization. No dose adjustment is necessary for VIS410 based on renal or hepatic impairment. For patients with renal insufficiency, refer to prescribing information for administration of oseltamivir.

VIS410 is a colorless to slightly yellow, clear to opalescent solution, essentially free of particles. VIS410 is formulated at a concentration of 25 mg/mL in 40-mM citrate-sodium phosphate, 150-mM sodium chloride, and 0.025% polysorbate 80.

The investigational product will be provided by the Sponsor. VIS410 will be supplied in Type I 20-mL glass vials containing a nominal 20-mL solution. A copy of the certificate of analysis of the investigational product will be sent to the clinical center.

The investigational drug product is manufactured by Lyophilization Services of New England in accordance with Good Manufacturing Practice as required by the current Good Clinical Practice (GCP). Manufacturing, packaging, and labeling of the investigational product, VIS410, is conducted under the responsibility of the Sponsor. The study drug will be labeled according to local law and regulatory requirements. Specific dilution procedures for VIS410 will be described in detail in the Pharmacy Manual.

Placebo will be a normal saline solution (0.9%) and will be prepared by the pharmacist.

7.2 Reference Product, Dose, Mode of Administration

Placebo (normal saline solution 0.9%) will be administered IV over 2 hours as a single 200-mL infusion, followed by a 25-mL (or volume equivalent to volume of IV line) saline flush to ensure all product is administered, in addition to oseltamivir (Tamiflu) 75 mg BID for total of 5 days (10 doses). Treatment with oseltamivir may be extended for up to 5 additional days (up to 20 doses of total therapy) if clinical symptoms warrant further treatment as assessed by the Investigator. For patients with renal insufficiency, refer to prescribing information for administration of oseltamivir. Note: based on SOC, subjects may have started oseltamivir therapy prior to randomization.

7.3 Instructions for Preparation, Use, and Administration

The required amount of VIS410 to be dosed (2000 mg or 4000 mg) will be diluted with normal saline up to a total volume of 200 mL. For placebo subjects, 200 mL of normal saline will be prepared. This infusion will be followed by a 25-mL (or if IV line volume is >25 mL, an equivalent volume) saline flush. The saline flush following administration will ensure all VIS410/placebo has been administered.

The study infusion will be administered IV using a 0.22- μ m in-line filter and will be controlled by a volumetric pump. Standard, infusion lines will be used, and microfilters will be provided by the Sponsor as appropriate.

The infusion bag will be covered with an opaque sleeve in the pharmacy to maintain the study blind. The VIS410/placebo will be administered IV at a rate of 100 mL/h, over 2 hours.

When 200 mL has been administered, the line will be flushed with normal saline. The infusion time may be longer at the Investigator's discretion based only on local infusion site-related symptoms up to a maximum of 4 hours.

Refer to the Pharmacy Manual for directions on storage, handling, stability data, preparation, and use. For more detailed information on VIS410, refer to the current Investigator's Brochure.⁸

